### **8.8 Reference to Declaration of Helsinki/Basic Principles**

The study procedures outlined in this protocol will be conducted in accordance with the US CFR governing Protection of Human Subjects (21 CFR 50), Financial Disclosure by Clinical Investigators (21 CFR 54), IRBs (21 CFR 56), Investigational New Drug Application (21 CFR 312), Applications for FDA Approval to Market a New Drug (21 CFR 314), and Radioactive Drugs For Certain Research Uses (21 CFR 361.1), as appropriate. As such, these sections of US Title 21 CFR, along with the applicable International Conference on Harmonisation Guidelines, are commonly known as Good Clinical Practices, which are consistent with the Declaration of Helsinki.

### **8.9 Financing and Insurance**

Financing and insurance will be addressed in a separate agreement.

---

## APPENDIX A - CLINICAL LABORATORY EVALUATIONS

Clinical Chemistry Panel (Fasted):	Complete Blood Count:	Urinalysis:
Alanine aminotransferase	Hematocrit	Bilirubin
Albumin	Hemoglobin	Color and appearance
Alkaline phosphatase	Mean corpuscular hemoglobin	Glucose
Aspartate aminotransferase	Mean corpuscular hemoglobin concentration	Ketones
Blood urea nitrogen	Mean corpuscular volume	Leukocyte esterase
Calcium	Platelet count	Nitrite
Chloride	Red blood cell (RBC) count	Occult blood
Cholesterol	RBC distribution width	pH and specific gravity
Creatinine	White blood cell (WBC) count	Protein
Glucose	WBC differential (absolute):	Urobilinogen
Iron	Basophils	Microscopic exam including
Phosphorus	Eosinophils	bacteria, casts, crystals,
Potassium	Lymphocytes	epithelial cells, RBCs, and
Sodium	Monocytes	WBCs (if protein, leukocyte
	Neutrophils	esterase, nitrite, or blood is
		positive)
Total bilirubin		
Total protein		
Triglycerides		
Uric acid		
Drug Screen:	Other Tests:	Hormone panel – females only:
Including but not limited to the following:	Hepatitis B surface antigen	Follicle-stimulating hormone (postmenopausal females only)
Alcohol (ethanol; via breathalyzer; at Check-in only)	Hepatitis C virus antibody	Serum pregnancy test (human chorionic gonadotropin)
Amphetamines	Human Immunodeficiency Virus antibody	
Barbiturates		
Benzodiazepines		
Cannabinoids		
Cocaine (metabolite)		
Methadone		
Opiates		
Phencyclidine		
Cotinine		

---

**APPENDIX B - BLOOD SAMPLING SUMMARY**

Purpose	Maximum Blood Volume per Sample (mL)	Maximum Number of Blood Samples	Maximum Total Volume (mL)
Serology	4	1	4
Pharmacokinetic and total radioactivity sampling	10	23	230
Metabolism sampling	10	7	70
Clinical laboratory tests	8	4	32
Pregnancy tests	4	2	8
FSH tests	4	1	4
Total			348

## APPENDIX C - ADVERSE EVENTS

### 1 ADVERSE EVENTS

#### 1.1 Definition of Adverse Events

An adverse event (AE; or adverse experience) is defined as any untoward medical occurrence experienced by a patient or healthy subject, whether or not considered drug related by the Investigator (or designee). A treatment-emergent AE is an AE that is reported after a dose of study drug.

The following are all AEs:

- unfavorable changes in general condition;
- subjective or objective signs/symptoms;
- concomitant diseases or accidents;
- clinically relevant adverse changes in laboratory parameters observed in a subject during a clinical study.

Adverse events comprise all disturbances of general health status, subjective and objective disease symptoms (including laboratory abnormalities), and accidents observed in the context of a clinical trial, irrespective of a possible causal relationship with the administration of the trial substance. Events occurring in the framework of a clinical trial during drug-free and post-treatment periods, under placebo, or in a reference group receiving drug or nondrug therapy are also to be designated as AEs.

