h A baseline version of the C-SSRS survey will be given at Screening and the “since last visit” version of the C-SSRS will be given at Check-in, on Day 2, and at Discharge.

i Vital sign measurements (oral temperature, respiratory rate, and seated blood pressure and pulse) will be obtained at single timepoints at Screening, Check-in, and at 1, 2, 4, 24, 48, 72, 96, 120, 168, and 192 hours postdose. If the subject is not discharged on Day 9, additional vital sign measurements will be performed every 24 hours until Discharge. Vital sign measurements will be performed with the subject in a seated position after the subject has rested for at least 5 minutes. When the timepoints for blood draws and vital sign measurements coincide, the vital sign measurements will be collected prior to the blood draws and as close to the scheduled timepoint as possible.

j Orthostatic blood pressure and pulse will be obtained at Screening, Check-in, at 0 Hour (predose), and at 1.25, 1.75, and 2.25 hours postdose. Blood pressure and pulse will first be collected with the subject in a seated position after the subject has rested for at least 5 minutes. Blood pressure and pulse will be taken again after the subject has been standing for 2 to 4 minutes. The same arm will be used during each assessment of blood pressure and pulse. When the timepoints for blood draws and orthostatic vital sign measurements coincide, the orthostatic vital sign measurements will be collected prior to the blood draws and as close to the scheduled timepoint as possible.

k Single 12-lead ECGs obtained at Screening, Check-in, and Discharge. The 12-lead ECGs will be collected after the subject has been resting in a supine position for at least 10 minutes. When the timepoints for blood draws and ECGs coincide, the ECGs will be collected prior to the blood draws and as close to the scheduled timepoint as possible.

l Any SAEs occurring after the subject signs the Informed Consent Form will be recorded.

m Subjects will be monitored for AEs beginning at initiation of study drug. An AE inquiry will be performed at each postdose vital sign measurement.

n Single oral dose of [C]-lasmiditan at 200 mg (approximately 100 µCi) administered orally to subjects in a fasted state.

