### **6.5.1 Adverse Events**

Adverse event definitions (assignment of severity, causality, action taken, and outcome) and procedures for reporting serious AEs are detailed in [Appendix C](#).

Subjects will be asked a nonleading question such as “Have there been any changes in your health status since Screening/since you were last asked?” at the timepoints specified in [Table 6-1](#) to assess for the occurrence of AEs. Subjects will also be encouraged to voluntarily report AEs occurring at any other time during the study.

All nonserious AEs, whether volunteered, reported during AE inquiries, or noted on physical examination, will be recorded from initiation of study drug until study completion. Nonserious AE information should also be collected from the start of a washout period or other observational period intended to establish a baseline status for the subjects. Serious AEs will be recorded from the time the subject signs the ICF until study completion.

All AEs (nonserious and serious) should be followed until the event has resolved, returned to baseline, or is assessed as stable by the Investigator (or designee).

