10.4 Safety and Tolerability Assessments

10.4.1 Adverse Events

All AEs will be listed. The TEAEs will be summarised by treatment, severity, and relationship to the study drug. The frequency (the number of TEAEs, the number of subjects experiencing a TEAE, and the percentage of subjects experiencing a TEAE) of TEAEs will be summarised by treatment, and by Medical Dictionary for Regulatory Activities system organ class and preferred term. The summary and frequency TEAE tables will be presented for all causalities and for those TEAEs considered related to the study drug (those that have a relationship of reasonable

possibility). Any severe or serious AEs will be tabulated. For any AEs that change severity ratings the AE will be included only once under the maximum severity rating in the summaries.

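### Treatment-emergent AEs are defined by when they are reported, not when they began, so a complaint that started before dosing can enter the all-causality TEAE tables

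*Protocol*

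**What the plan says.** The definition is in Protocol Appendix C 1.1: "A treatment-emergent AE is an AE that is reported after a dose of study drug". The SAP spells out the abbreviation TEAE in its section 3 but does not define the term. SAP section 12 declares no departures from the protocol's analyses, so the protocol definition carries over.

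SAP 10.4.1 builds its summaries on this unit: "The TEAEs will be summarised by treatment, severity, and relationship to the study drug". Frequencies are also given by system organ class and preferred term, as the number of events and the number and percentage of subjects. The tables are produced once for all causalities and once for events judged related.

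On collection, the footnote to the AE row of Table 6-1 says: "Subjects will be monitored for AEs beginning at initiation of study drug. An AE inquiry will be performed at each postdose vital sign measurement". The postdose vital-sign times in the same table are "at 1, 2, 4, 24, 48, 72, 96, 120, 168, and 192 hours postdose", so the first inquiry falls at 1 hour. The AE row is blank at Screening and Check-in; only SAE monitoring runs from consent.

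Protocol 6.5.1 offers this example of a nonleading question: "Have there been any changes in your health status since Screening/since you were last asked". The same section says that nonserious AEs "will be recorded from initiation of study drug until study completion", and then adds: "Nonserious AE information should also be collected from the start of a washout period or other observational period intended to establish a baseline status".

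**The concern.** A treatment-emergent event should be one that began, or got worse, after exposure. The protocol's rule turns on the time of the report instead. Report time and onset time can differ here because nobody is scheduled to ask about AEs until an hour after the dose, and the question then asked may cover time before the dose.

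Safety and tolerability is a secondary objective, and the TEAE tables are its main numerical summary. There are 8 subjects and no control group against which background complaints would cancel out. Protocol 2.1.2 lists tiredness, drowsiness, dizziness and paresthesia as the most frequent AEs with lasmiditan. Some of these, tiredness above all, are also complaints a healthy volunteer might have after a fast of at least 10 hours and days without caffeine. A predose complaint of that kind would not stand out in a frequency table.

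The rule is also silent on the reverse case: a condition known before dosing that worsens afterwards.

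**Working it through.** The documents state no figure on this point, so there is nothing to reproduce. The check sets the provisions side by side and then sizes the effect.

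**Step 1: follow one event through the rules.** A nonserious complaint starts on the evening of Day -1, after the Check-in history has been taken.

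- Before dosing: no AE inquiry is scheduled (Table 6-1, AE row).
- 1 hour postdose: first inquiry. If the example question is used in its since-Screening form, the subject can properly mention the complaint.
- Classification: the event is reported after the dose, so it meets Appendix C 1.1. No onset test removes it.
- Causality: Appendix C 1.2 judges relatedness on the timing of AE onset relative to administration. A complaint known to predate the dose should be rated as having no reasonable possibility of being drug-related.
- Tables (SAP 10.4.1): it is counted in the all-causality frequency and severity tables. It should not appear in the related-TEAE tables.

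**Step 2: how far back the exposure runs.** Screening spans Days -29 to -2. Table 6-1 schedules an interim medical history on Day -1, so complaints arising during screening have a planned capture point before dosing. What remains is the time from that history to the dose on Day 1, plus anything the history missed. No rule takes a complaint already in the history out of the TEAE count if the subject reports it again after dosing.

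**Step 3: size per subject.** The Safety Population is everyone dosed with at least one postdose safety assessment, so N = 8 if all planned subjects are dosed. The target of at least 6 completers does not shrink this denominator.

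- Event count: each misclassified event adds 1.
- Subject incidence: it rises by 1/8 = 12.5 percentage points if the subject has no true postdose event in the same category, and by 0 if the subject does.

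**Step 4: chance of at least one affected subject.** The documents give no rate for such complaints. Let p be an assumed probability per subject, independent across subjects. The chance is 1 − (1 − p)^8 and the expected number is 8p.

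| Assumed p | Chance of at least one of 8 | Expected number |
|---|---|---|
| 2% | 1 − 0.98^8 = 15% | 0.16 |
| 5% | 1 − 0.95^8 = 34% | 0.4 |
| 10% | 1 − 0.90^8 = 57% | 0.8 |
| 20% | 1 − 0.80^8 = 83% | 1.6 |

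These rows show scale only. Being affected does not always move a percentage, for the reason in Step 3.

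**The case against.** The case for leaving the text alone has several parts.

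- **Causality is judged on onset.** A reader might infer that predose complaints would be attributed to the drug and contaminate every TEAE table. Appendix C 1.2 does not support that. If it is followed, the related-TEAE tables are largely protected. This stands, and it limits the point to the all-causality tables.
- **The lookback is shorter than it appears.** A reader might infer a routine recall period of about four weeks, driven by a fixed script. Protocol 6.5.1 gives the question only as an example, with since-last-asked as an alternative wording, and the Day -1 history captures complaints from the screening period. This also stands.
- **Recording starts at dosing.** The statement that nonserious AEs "will be recorded from initiation of study drug until study completion" could be read as an onset limit. The text does not say so, and two programmers could classify the same event differently.
- **A baseline period is mentioned.** The sentence beginning "Nonserious AE information should also be collected from the start of a washout period or other observational period intended to establish a baseline status" could put predose complaints on record before the dose. But no such period is named, and Table 6-1 schedules no predose inquiry. The help is partial at best.
- **The consequence is small.** The study has one arm, all safety output is descriptive, any such error overcounts TEAEs, and SAP 10.4.1 lists every AE, so the few events can be reviewed one by one. This is true and bears on priority. It does not make the tabulated counts right.
- **The table shells may hold a rule.** SAP section 4 refers to a separate shell document, which is not available here. That cannot be checked.

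**Conclusion.** The point holds within limits. The only stated definition classifies by report time, and the collection schedule lets that differ from onset. Applied as written, the rule counts a predose-onset nonserious complaint, first reported after dosing, in the all-causality TEAE frequency and severity tables. The exposure is mainly Check-in to dosing, plus whatever the Day -1 history missed.

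The size is up to 12.5 percentage points of incidence per misclassified subject. That assumes all 8 subjects are in the Safety Population and that the subject has no true postdose event in the same category. How often this would happen is unknown; the probabilities above rest on assumed rates and should not be read as estimates for this study.

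The documents do not support a claim that drug-related AE rates would be materially wrong. PK and recovery results are unaffected. This is a modest error in a stated rule, worth correcting because the correction is simple.

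**What to change.** In SAP 10.4.1, define a TEAE as an AE with onset at or after dosing, or one present before dosing that worsens after it, based on the recorded onset date and time. List earlier-onset events separately as non-treatment-emergent. Record the change in SAP section 12, which now states that there are none, and align Protocol Appendix C 1.1.

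The cost is one SAP definition, a programming rule, the section 12 entry and a protocol wording change, which Protocol 8.1 makes subject to agreement between the sponsor and the investigator. No new study procedure is needed, provided the CRF captures AE onset date and time; the documents do not show the form.

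The downside is that a convention is needed for missing onset times on Day 1, the one day on which the date alone cannot settle the classification. Judging worsening also needs some record of predose severity, and the documents do not say whether the medical history carries one.

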#### 1.2 Categorization of Adverse Events

The severity of AEs will be categorized as follows:

- **MILD** = of little concern to the subject and/or of no clinical significance, is not expected to affect the subject's health or well-being;
- **MODERATE** = discomforting enough to cause interference with or change in usual activities, is likely to require medical intervention or close follow-up;
- **SEVERE** = incapacitating or causing inability to work or participate in many or all usual activities, is of concern to the subject or poses substantial risk to the subject's health or

well-being, is likely to require medical intervention or close follow-up.

The Investigator (or designee) will make a determination of the relationship of the AE to the study drug using a 2-category system according to the following guidelines:

- **Reasonable Possibility** = a plausible temporal relationship exists between the AE onset and administration of the investigational product, and the AE cannot be readily explained by the subject's clinical state or concomitant therapies. Furthermore, the AE appears with some degree of certainty to be possibly related, based on the known therapeutic and pharmacologic actions or AE profile of the investigational product. In case of cessation or reduction of the dose, the AE may abate or resolve and it may reappear upon rechallenge.
- **No Reasonable Possibility** = evidence exists that the AE has an etiology other than the investigational product and/or no plausible temporal relationship exists between the AE onset and administration of the investigational product. For SAEs, an alternative causality must be provided (e.g., pre-existing condition, underlying disease, intercurrent illness, or concomitant medication).

An AE is associated with the use of the drug if there is a reasonable possibility that the experience may have been caused by the drug.

The following categories will be used for the action taken with the study drug for the AE: drug withdrawn, dose not changed, drug interrupted, unknown, and not applicable.

The following categories will be used for the outcome of the AE: resolved, resolved with sequelae, ongoing, fatal, and unknown.

### 1.3 Pregnancy

As information is available, a pregnancy diagnosed during the study will be reported immediately to the Investigator (or designee) or Sponsor, including pregnancy in female partners of male subjects. The pregnancy may be followed to term or outcome and this outcome may be reported to the Sponsor. Pregnancy, in and of itself, is not regarded as an

AE or serious AE (SAE) unless the birth results in a congenital anomaly/birth defect or there is suspicion that the study medication may have interfered with the effectiveness of a contraceptive medication or method.

#### **1.4 Definition of Serious Adverse Events**

An SAE (by Food and Drug Administration [FDA] definition) is any adverse drug experience occurring at any dose that results in any of the following outcomes:

- death;
- a life-threatening adverse drug experience (i.e., places the subject, in the view of the Investigator (or designee), at immediate risk of death);
- inpatient hospitalization or prolongation of existing hospitalization;
- a persistent or significant disability/incapacity;
- a congenital anomaly/birth defect;
- important medical event that may require medical or surgical intervention to prevent one of the above outcomes.

Important medical events that may not result in death, be life-threatening, or require hospitalization may be considered SAEs when, based on appropriate medical judgment, they may jeopardize the patient or subject and may require medical or surgical intervention to prevent one of the outcomes listed in this definition. All SAEs must be collected that occur after the subject signs the Informed Consent Form.

#### **1.5 Unexpected Adverse Drug Experience**

An unexpected adverse drug experience is any adverse drug experience, the specificity or severity of which is not consistent with the current Investigator Brochure (IB) or, if an IB is not required or available, the specificity or severity of which is not consistent with the risk information described in the general investigational plan or elsewhere in the current application, as amended.

#### **1.6 Reporting**

Food and Drug Administration-reportable AEs are AEs that are associated with the use of the drug and are serious and unexpected. Food and Drug Administration-reportable AEs will be reported by the clinical site to the Sponsor, Medical Monitor assigned by the Sponsor, and the responsible Institutional Review Board (IRB).

The Sponsor and Medical Monitor will be notified in writing (e.g., facsimile) within 24 hours of when an AE that is potentially FDA-reportable is first recognized or reported.

Subsequently, a written confirmation or summary of the AE (using FDA Form 3500A, or equivalent) will be sent to the Sponsor within 3 working days of the original notification. (Instructions for completion of FDA Form 3500A may be obtained from the FDA website at [www.fda.gov/medwatch/how.htm](http://www.fda.gov/medwatch/how.htm)).

The IRB will be notified of any FDA-reportable AE within the timeframe required by the IRB. The IRB Serious and Unexpected Adverse Experience Submission Form will be completed and submitted with the copy of the written confirmation or summary of the AE.

3 ABBREVIATIONS

Abbreviations pertain to the SAP only (not the TFLs).

ADaM	analysis data model
AE	adverse event
CDISC	Clinical Data Interchange Standards Consortium
CRF	Case Report Form
CSR	Clinical Study Report
C-SSRS	Columbia Suicide Severity Rating Scale
CV%	coefficient of variation
EC	Early Clinical
ECG	electrocardiogram
ICH	International Conference on Harmonisation
MedDRA	Medical Dictionary for Regulatory Activities
QTc	QT correction; QT interval corrected for heart rate
QTcF	QTc calculated using the Fridericia correction
SAP	Statistical Analysis Plan
TEAE	treatment-emergent adverse event
TFLs	tables, figures, and listings
$\%AUC_{\text{extrap}}$	percentage of AUC that is due to extrapolation from the time of the last quantifiable concentration to infinity
$\%FR$	Percent of dose recovered in feces over a sampling interval
$\%UR$	Percent of dose recovered in urine over a sampling interval
$AUC_{0-\infty}$	area under the concentration-time curve from time zero to infinity
$AUC_{0-\text{tlast}}$	area under the concentration-time curve from time zero to the time of the last quantifiable concentration
A_{ef}	Amount excreted in feces over a sampling interval
A_{eu}	Amount excreted in urine over a sampling interval
BLQ	below the limit of quantification
BMI	body mass index

CL/F	apparent total clearance
C _{max}	maximum observed plasma concentration
CL _R	Renal clearance
LLOQ	lower limit of quantification
LS	least squares
PK	pharmacokinetic
PT	preferred term
R ² -adjusted	adjusted coefficient of variation for goodness of fit
SD	standard deviation
SOC	system organ class
t _{1/2}	apparent terminal elimination half-life
t _{last}	Time of last quantifiable concentration
t _{max}	time of maximum observed concentration
TRA	total radioactivity
V _z /F	apparent volume of distribution during the terminal phase

